The suggested sample size for DCE surveys is estimated by the method of Orme and Johnson as N >500c/(t x a), where c is the number of analysis cells (i.e., the largest number of levels for any attribute), t is the number of choice tasks, and a is the number of options. Assuming maximum 4 levels per attribute, 10 choice tasks, and 3 options, the minimum required sample size is 67 to examine the effects in the overall study population. However, a larger sample size is necessary to measure preference heterogeneity among patients participants. Thus, administering the DCE questionnaire to all nested cohort participants is being proposed to fully assess preference heterogeneity in the patient population.

For our qualitative and costing components, we have not calculated sample sizes *a priori*, as we will not be conducting statistical hypothesis testing. The total participants listed in Table 5 (below) are meant to serve as a guide only. Additional IDIs, FGDs/ implementation surveys, KIIs, and structured observations may be added until thematic saturation is reached and no new themes are elicited from participants.

vi. Recruitment & Enrolment

For the cross-sectional patient surveys, we will coordinate with facility staff to approach, in person, consecutive PLHIV accessing routine health services at the clinic about the study. We will sensitize patients about the study at the clinic appointment desk, triage, and other waiting areas to take advantage of times when patients are queueing or otherwise awaiting health services. We will seek to conduct study activities after patients have received most of their clinic services so as not interrupt routine work and patients flows. After written informed consent procedures are completed, we will request basic locator information (e.g. phone number) to follow up with participants and administer a brief, one-time bio-behavioral survey.

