We anticipate needing to complete the following number of qualitative data collection activities (Table 5, below) with the following number of participants: 1) For IDIs, ~20 cohort participants will be interviewed to explore their experiences with both usual practice and TASKPEN (~10 IDIs per facility). These participants will be purposively selected to ensure balance in gender, age band, and NCD comorbidities; 2) For FGDs, ~4 total FGDs (or ~2 FDG per site) involving ~4-8 non-physician health workers OR ~4-8 community health workers/ lay health providers per FGD following TASKPEN implementation (or ~16-32 total participants); and 3) For KIIs, interviews with ~10 key stakeholders will be performed, including ART and OPD clinic managers/ in-charges or designee and policy makers at provincial and national MOH levels, selected purposively based on their involvement and familiarity with TASKPEN implementation and/or the NCD policy setting in Zambia. For all the above-mentioned qualitative data collection activities, we will adapt the semi-structured tools from specific objective #1 based on the CFIR and formative research findings from that objective to create the tools for specific objective #2. Finally, we will administer the same implementation survey used in objective #1 (with the addition of a clinical sustainability assessment) to FGD participants to assess measures of acceptability, appropriateness, feasibility, and sustainability. We anticipate conducting qualitative and mixed methods data assessment after both sites are exposed to the TASKPEN intervention in the mini stepped wedge pilot.

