All qualitative data collection activities for specific objective #2, will be adapted from the semi-structured tools used in specific objective #1 that are based on the CFIR and formative research findings from that objective. IDI guides, as well as the WHOQOL-HIV-BREF-Zam, will be developed in English and translated into *Bemba* and *Nyanja*, the two other languages that are commonly spoken in Lusaka. FGD and KII guides will be developed and administered in English since these participants speak and write fluently in English, which is the official language of health training in Zambia. IDI, FGD and KII guides may undergo minor adaptation over the life of the study to optimize participant comprehension and thematic elicitation, and to minimize any risk of psychosocial distress posed by the wording of questions and probes. Audio recording will also be used with the consent of participants. Verbatim transcripts will be transcribed and translated into English (as needed). Field guides will be piloted before data collection begins, and the tools will be further refined to improve their clarity, completeness, overall usability. Electronic devices used for data collection will be password-protected, with access restricted to authorized and trained study staff only. For sharing and analysis purposes, individual identifying information will be removed and where necessary, codes will be used. Standard operating procedures will be developed to guide and inform the usage of the developed tools.

At the conclusion of each FGD, we will administer an implementation survey incorporating three empirically supported measures for the acceptability, feasibility, and appropriateness of the final TASKPEN intervention. ⁹⁸ Each measure contains 4 questions (i.e., 12 total) that are scored on a Likert scale from 1 (completely disagree) to 5 (completely agree) that ask respondents to rate the TASKPEN intervention on the aforementioned implementation domains. We will also incorporate the Clinical Sustainability Assessment Tool, which contains 35 items on 1 (To little or no extent) to 7 (To a very great extent) Likert scale to assess perceived sustainability of the TASKPEN intervention.

vi. Laboratory procedures

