The primary measures for the pilot are adoption, acceptability, feasibility, appropriateness, as well as the preliminary effect of the TASKPEN intervention. We will assess implementation outcomes principally using a handful of theoretical frameworks. A brief questionnaire will be administered that will feature the simple 12-item implementation survey (incorporating empirically supported measures for acceptability, feasibility, and appropriateness) mentioned above, among other implementation-relevant items⁹⁸. We will further examine **acceptability** in our qualitative data as a construct comprising multiple dimensions⁹⁹. We will include open-ended questions guided by established implementation science frameworks such as the CFIR to elaborate on what makes the intervention appropriate or not and acceptable or not. We will further evaluate **feasibility** in our qualitative data by applying the theoretical basis of "compatibility" from Rogers' "Diffusion of Innovation" theory, among other theories¹⁰⁰.

We will describe implementation outcomes of **adoption** and **reach** according to RE-AIM. We will also calculate **retention** as the proportion of participants enrolled in the nested cohort and considered to be engaged in care at ~6 months. We will measure **adherence** in the nested cohort by reviewing pharmacy records at ~6 months to determine consistent access to anti-hypertensive, diabetes, and dyslipidaemia medications, as appropriate, as well as antiretroviral therapy. For the patient surveys, we will ask participants about adherence and review pharmacy records to examine medication adherence overall at the study sites.

Finally, we will pilot the feasibility, applicability, and completeness of the following measures in the cross-sectional assessments and nested cohort for adoption in the future follow-on trial:

- 1. **Dual** HIV and NCD disease control, defined as:
 - a. HIV RNA level of <200 copies per milliliter on the most recent measure; **AND**

- The absence of the following NCD conditions as defined by the nested cohort eligibility criteria:
 1) uncontrolled systolic hypertension;
 2) uncontrolled diabetes mellitus;
 and
 3) uncontrolled dyslipidaemia.
- 2. 10-year ASCVD risk score (based on American College of Cardiology/ American Heart Society guidelines)
- 3. The HIV-specific *D.A.D. CVD risk score*: (The Data-collection on Adverse Effects of Anti-HIV Drugs) score.
- 4. Quality of life as measured by WHOQOL-HIV-BREF ¹⁰¹.

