Using baseline, midline, and endline patient survey data and routine EMR data, we will assess the implementation outcomes described in Table 6. We will calculate standardized scores for validated instruments in our implementation survey. Comparisons of proportions for the aforementioned implementation outcomes will be done by calculating prevalence ratios and associated 95% confidence intervals as appropriate. Comparisons of continuous outcomes will be done by the Z-test/ 2-sample T-test or the Wilcoxon Rank-Sum test as appropriate.

To understand patient-level outcome measures of **disease control, retention**, **adherence**, and **viral suppression**, we will analyse data from the patient surveys. We will estimate **dual disease control** as the proportion of participants in the intervention and control periods who have a HIV viral load <200 copies/ml and do not have uncontrolled systolic hypertension, diabetes, and/or dyslipidaemia. We will calculate **retention** as the proportion of participants considered to be consistently engaged in care at 6 months according to the national HIV treatment program definition (e.g., without evidence of death, default, or loss to follow up defined as ≥30 days having elapsed since a missed pharmacy refill/ clinic visit). We will measure **adherence** in the nested cohort by reviewing pharmacy records at 6 months to calculate the medication possession ratio (MPR) over that time frame for anti-hypertensive, diabetes, and dyslipidaemia medications, as well as antiretroviral therapy. We will calculate **viral suppression** as the proportion of survey participants meeting established thresholds of suppression (e.g., viral load <1,000 copies/ml or <200 copies/ml) at 6 months following ART initiation and/or study enrolment. To compare outcome measures, we will report differences and ratios with accompanying 95% confidence intervals. We will compute variance for differences and ratios using the sandwich variance estimator or appropriate resampling approaches to account for the clustered nature of the data by site.

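### Implementation-survey scores from about four focus groups fall under two-sample tests that treat raters as independent, although the sample-size section disclaims hypothesis testing for that component

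*Combined protocol and SAP*

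**What the plan says.** All references are to section 8 of the combined protocol and SAP, Specific Objective #2, unless stated.

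- **Status of the outcomes.** Section e.vii (Outcomes) says: "The primary measures for the pilot are adoption, acceptability, feasibility, appropriateness", together with the preliminary effect of TASKPEN.
- **How they are scored.** Section e.v (Study instruments): "At the conclusion of each FGD, we will administer an implementation survey incorporating three empirically supported measures". On the scale: "Each measure contains 4 questions (i.e., 12 total) that are scored on a Likert scale from 1 (completely disagree) to 5 (completely agree").
- **Who rates.** Section e.iv (Qualitative and mixed methods data collection) plans about "4 total FGDs (or ~2 FDG per site"), "involving ~4-8 non-physician health workers OR ~4-8 community health workers/ lay health providers per FGD", "or ~16-32 total participants". Table 5 shows one non-physician health worker group and one community or lay health worker group at each site. The ratings are expected after both sites have been exposed to TASKPEN.
- **How they are analysed.** Section g.i says standardized scores will be calculated for the survey instruments. In the same paragraph: "Comparisons of continuous outcomes will be done by the Z-test/ 2-sample T-test or the Wilcoxon Rank-Sum test as appropriate". The significance threshold given earlier in g.i is 0.05.
- **Whether they are tested.** Section d.v gives no sample size for the qualitative and costing components, "as we will not be conducting statistical hypothesis testing". The same paragraph lists the focus groups with their implementation surveys among the activities covered, and says more may be added.

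**The concern.** People in one focus group work at the same facility in the same cadre, and they complete the survey just after a shared discussion. Their scores are likely to be correlated. A Z, t or rank-sum test on individual raters ignores this and understates the variance of any comparison between sets of groups. In the pilot, a site or cadre comparison has only two groups on each side.

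The one clustering provision in g.i does not cover the gap. The sandwich or resampling variance comes in the following paragraph, on patient-level outcomes. It clusters by site, of which there are two, and not by focus group.

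Sections d.v and g.i also give different rules for the same scores. An analyst following d.v would only describe them; one following g.i could test them. At stake is a reported difference between sites or cadres that reflects nothing more than variation between groups.

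**Working it through.** **Stated count.** 4 groups × 4 raters = 16 and 4 × 8 = 32, matching the plan's 16-32.

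**Assumptions.** The documents give no correlation for these ratings. Their only intraclass correlation is 0.25, in section d.v, for dual HIV/NCD control by site. I take a within-group correlation ρ of 0.05 to 0.25, with 0.25 as an assumed upper case. The contrast is two groups against two, with m = 4 to 8 raters per group. Scores are normal with total variance 1, there is no true difference, and the test is two-sided at 0.05.

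**Loss of information.** Design effect = 1 + (m − 1)ρ. At ρ = 0.25:

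- m = 4: 1 + 3 × 0.25 = 1.75, so 16 raters carry the information of 16/1.75 = 9.1.
- m = 8: 1 + 7 × 0.25 = 2.75, so 32 raters carry the information of 32/2.75 = 11.6.

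**The design balances one factor.** Each site has one group per cadre. A cadre effect common to both sites therefore cancels in a site contrast, and a facility effect common to both cadres cancels in a cadre contrast. Let f be the share of ρ due to the balanced factor. The true variance of the difference in means is

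ρ(1 − f) + (1 − ρ)/m.

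The rater-level t-test expects on average s²/m, where s² = [1 + (m − 1)ρ + 2(m − 1)(1 − ρ)]/(2m − 1).

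Worked case, m = 8 and ρ = 0.25: s² = (2.75 + 10.5)/15 = 0.883, so the test assumes 0.883/8 = 0.110. The true variance is:

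- f = 0: 0.25 + 0.094 = 0.344, about 3.1 times the assumed value.
- f = 0.5: 0.125 + 0.094 = 0.219, about 2.0 times.
- f = 1: 0.094, about 0.85 times, so the test is slightly conservative.

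**Simulated rejection rates, nominal 5% t-test, m = 4 to 8:**

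| ρ | f = 0 | f = 0.5 | f = 1 |
|---|---|---|---|
| 0.05 | about 7-9% | about 6-7% | below 5% |
| 0.10 | about 9-13% | about 7-9% | below 5% |
| 0.25 | about 15-26% | about 10-16% | below 5% |

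At ρ = 0 the t-test holds its level (4.8-4.9%). Choosing another of the named tests does not remove the problem: at ρ = 0.25 and f = 0 the Z-test rejects in 18-28% and the rank-sum test in 12-24%.

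**One mean per group.** With f = 0, a t-test on the four group means rejects in about 5% at every ρ tried. It has 2 degrees of freedom and a critical value of 4.30. The difference detectable with 80% power, for ρ from 0 to 0.30, is 2.8-3.9 SD (m = 4) or 2.0-3.5 SD (m = 8). Treating raters as independent suggests 1.51 and 1.02 SD. Four groups can be split two against two in 6 ways, so an exact permutation test cannot give a two-sided p below 2/6 = 1/3.

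**The case against.** The strongest reply is that no site or cadre comparison of these scores is planned. Section g.i opens that paragraph with patient-survey and medical-record data, commits only to scoring the staff instruments, and applies the tests to continuous outcomes in general, as appropriate. The pilot ratings have no control-period counterpart. Section d.v then disclaims testing. Much of this stands: a reader might infer that the plan commits to testing site against site, and it does not say so. But the staff scores are the continuous outcomes named just before the tests, and nothing in g.i excludes them. A disclaimer in the sample-size section does not override an instruction in the analysis section.

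The second reply is that independent group effects overstate the error, because cadre or facility is balanced. This stands, and it is why the table has three columns. The balanced share is unknown.

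Third, the Objective #1 focus-group text has participants respond mainly to the moderator, and those tools are to be adapted for Objective #2. That may weaken peer influence, but participants still hear one another and still share a facility and cadre.

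Fourth, four is an approximate number and groups may be added. More groups would help a group-level analysis, but would not repair a test that ignores grouping. If Objective #1 were compared with Objective #2 (nine groups against four), the t-test would still reject in 7-16% (m = 4) or 9-27% (m = 8) for ρ of 0.05 to 0.30 with independent group effects.

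**Conclusion.** The point holds in a limited form. Sections d.v and g.i conflict on whether implementation-survey scores are tested. If g.i is followed for them, raters are treated as independent when they are grouped. The size depends on an unstated contrast, an assumed correlation and an unknown balanced share. For a pilot site or cadre contrast it runs from no inflation (all of the correlation balanced) to 15-26% false positives (correlation 0.25, none balanced). At a correlation of 0.05 the excess over 5% is under 5 percentage points in every case.

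Two stronger readings are not supported. A reader might infer that the answer to the main study question is at risk. That question is whether task-shifting is feasible, acceptable and appropriate; it turns on the level of the ratings and on the qualitative data, not on a site or cadre p-value. A reader might also take 15-26% as the expected error. It rests on a correlation stated for a different outcome and a different cluster, and on no balancing.

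**What to change.** In section g.i, state that the Z, two-sample t and rank-sum tests do not apply to implementation-survey scores, which brings it into line with section d.v. Report each focus group's mean score on the three measures, and the range of those means by site and cadre. If any test is kept, name the contrast, use one mean per focus group as the unit, and say that four groups give very low power.

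Leave the survey at the end of the discussion. Moving only the Objective #2 survey ahead of it would break comparability with the Objective #1 survey, which is also given afterwards.

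The cost is a few sentences of analysis text and no change to data collection. The downside is that there will be no usable p-value for site or cadre differences in these scores.

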Nested cohort participants will be the only study participants having more than one encounter with the study team. As such, we will schedule study follow-up visits approximately every 3 months over a ~9-month period starting at 2 weeks from the time of the baseline patient survey. Thus, their total engagement with the study will amount to about 4 follow-up visits (at ~2 weeks and then around 3 and 6 months from the baseline survey plus one study exit visit at around 9 months). Study visits will be largely aligned with the schedule of routine clinic visits stipulated in the Zambia national HIV guidelines (i.e., every 3-6 months for established ART patients and more frequently during the first month of treatment for new ART patients) and will be scheduled mostly for times when the study teams are conducting the midline and endline surveys at the study sites. Study research assistants, who are not

providing any interventions as part of TASKPEN, will contact the participants in the nested cohort via phone call every month to check vital and clinic status (still in care at original site) and ascertain any changes in household location. If the participant is unreachable, community tracing will be done to verify whereabouts leveraging existing CIDRZ community tracing platforms in Lusaka. At the next time a survey assessment is done at the site, and before the clinic is switched from control to intervention, the nested cohort participants will be re-assessed by the team.

Study follow-up procedures will be designed so as not to disrupt routine care delivery and will include: determination of retention in integrated HIV/NCD care and referral for routinely available adherence and psychosocial counselling and back-to-care services, as appropriate; lab monitoring for cardio-metabolic NCDs (see laboratory procedures below) if not already done by the government health workers during their routine health visits; brief survey administration to assess adherence, nutritional status, tobacco and alcohol use, and other NCD-related health parameters; and completion of the quality of life and DCE questionnaires.

e. Data collection plan and tools

Data collection overview

As in specific objective #1, data collection activities for specific objective #2 will involve a combination of NHSR and implementation research activities detailed below.

ii. Non-human subjects research activities

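### Six-month retention cannot register appointments missed at about month 6, because the loss rule needs a further 30 days; the nested cohort's existing 9-month follow-up could close the gap

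*Combined protocol and SAP*

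**What the plan says.** Section g.i defines retention as the share of participants "consistently engaged in care at 6 months according to the national HIV treatment program definition", for example "without evidence of death, default, or loss to follow up", the last of these being "loss to follow up defined as ≥30 days having elapsed since a missed pharmacy refill/ clinic visit". Default is not defined, and the national definition is not reproduced. Section e.vii (Outcomes measurement) gives the same time point and names the population: "the proportion of participants enrolled in the nested cohort and considered to be engaged in care at ~6 months". Section g.i instead introduces its patient-level outcomes, retention among them, with "we will analyse data from the patient surveys".

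Section d.vii (Nested cohort follow-up procedures) gives routine clinic visits as "every 3-6 months for established ART patients". Cohort study visits are at about 2 weeks, 3 months and 6 months, "plus one study exit visit at around 9 months". Between visits, research assistants telephone cohort members monthly to learn whether they are alive and still attending, and those who cannot be reached are traced in the community. Determining retention is listed among the follow-up procedures, with no visit excluded. No section defines a retention analysis at 9 months, and none states a refill interval.

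**The concern.** A missed-appointment rule with a grace period can register a loss only if the appointment falls due at least one grace period before the reading. Here the reading is at month 6, the grace period is 30 days, and the longest routine interval is 6 months. Both a 3-monthly and a 6-monthly schedule place an appointment at about month 6. A permanent miss at that appointment leaves the participant classed as retained unless something else reveals the loss.

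The measure is then least sensitive in those with the most widely spaced appointments, and the overall figure depends partly on the mix of schedules. The pilot is meant to inform a larger trial in which retention in care is a named outcome, so an optimistic figure could mislead its planning.

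**Working it through.** The plan states no retention rate, so there is no figure to reproduce. The check is calendar arithmetic.

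Inputs:
- Reading: month 6 (sections g.i and e.vii).
- Grace period: 30 days (section g.i).
- Visit interval: 3 to 6 months (section d.vii).
- Last cohort contact: about month 9 (section d.vii).
- Clock start: the baseline survey. Section d.vi recruits people attending for routine services, preferably once most of that day's care is done. That the next interval starts that day is my assumption.
- One month = 365.25/12 = 30.44 days, so month 6 is day 182.6 and month 9 is day 273.9.

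Earliest day on which a miss counts = due day + 30.

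| Appointment missed | Due day | Counts from day | Countable at month 6? |
|---|---|---|---|
| 3-monthly, first | 91.3 | 121.3 | yes |
| 4-monthly, first | 121.8 | 151.8 | yes |
| 5-monthly, first | 152.2 | 182.2 | just |
| 3-monthly, second | 182.6 | 212.6 | no |
| 6-monthly, first | 182.6 | 212.6 | no |

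The longest interval that works is (182.6 − 30)/30.44 = 5.01 months. By month 9 every row is countable: a month-6 miss has been classifiable for 273.9 − 212.6 = 61.3 days.

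Sensitivity to the unstated inputs:
- If refills are 3-monthly although visits are 6-monthly, a missed first refill counts from day 121.3.
- If a 6-monthly participant is surveyed x months after the visit that set the schedule, a miss counts from month 6.99 − x. That is month 5.99, 4.99 or 3.99 for x = 1, 2 or 3, so the problem disappears from about one month on.

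Illustration of size. Assume each due visit is missed for good with probability d, a share p of participants is seen 6-monthly and the rest 3-monthly, refills match visits, and only the 30-day rule detects loss.
- Countable at month 6: (1 − p)d.
- All misses due by month 6: (1 − p)[1 − (1 − d)²] + pd.
- Uncounted: (1 − p)(1 − d)d + pd.

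| d | p | Countable | Due by month 6 | Uncounted |
|---|---|---|---|---|
| 10% | 25% | 7.5% | 16.75% | 9.25% |
| 10% | 50% | 5.0% | 14.5% | 9.5% |
| 10% | 75% | 2.5% | 12.25% | 9.75% |
| 5% | 50% | 2.5% | 7.4% | 4.9% |

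The uncounted share is close to d whatever p is, because on both schedules everyone still attending has an appointment at month 6. These are upper-end values: any other route to detection, or a shorter refill interval, lowers them.

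**The case against.** The strongest reply is that the 30-day rule is one criterion among several. Death and default also count, and section g.i offers the whole list as an example of a national definition not shown. For the cohort, monthly calls and tracing could find someone out of care well before a 6-month appointment falls due. This stands, and it rules out the inference that a 6-monthly participant cannot be counted as lost, or that the figure is too high by construction. It does not remove the point: no section says that call or tracing results enter the retention classification, and default is undefined.

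Second, the rule covers refills as well as visits, and the clock start is assumed. Both stand. The arithmetic binds only where visit and refill are both due at about month 6.

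Third, a reader might take the gap between 14.5% and 5.0% as loss already incurred but hidden. It is not: with d = 10% and p = 50% the gap is 0.5 × 0.9 × 0.1 + 0.5 × 0.1 = 9.5%, made up wholly of misses assumed to fall on the reading day. Any fixed-date measure with a grace period lags in this way. The table shows what the reading leaves out, not an estimate of bias.

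Two further inferences go beyond the documents. One is that TASKPEN alters visit spacing and so distorts the comparison of control and intervention periods. Visit frequency is an attribute of the discrete choice experiment, and nothing says the intervention changes it. The other is that the 9-month visit plays no part in retention. Section d.vii lists determining retention without excluding that visit; what is absent is a named analysis.

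**Conclusion.** The point holds in limited form. Nested cohort participants whose next visit and refill are both due at about month 6 cannot meet the 30-day criterion at the 6-month reading. Month-6 misses among 3-monthly participants cannot be counted then either. Intervals up to about 5 months cause no difficulty for the first appointment. Six-month retention may therefore be overstated, unless death, default, an earlier refill, or the calls and tracing reveal the loss.

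The size cannot be computed from the documents. The illustrative 5 to 10 percentage points rests on assumed miss rates of 5% to 10%, refills matching visits, the clock starting at the survey, and no other detection. Retention is not among the primary measures listed in section e.vii, and the cohort carries no a priori hypothesis test. This is a worthwhile repair to a descriptive measure, not a threat to the pilot's main conclusions.

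**What to change.** In sections e.vii and g.i, for the nested cohort only:
- Add a retention measure covering visits and refills due by month 6, classified from records through the exit visit at about 9 months under the same 30-day rule.
- Report it by scheduled visit and refill interval, beside the 6-month figure.

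The cost is mainly wording. The exit visit is already planned and cohort members' routine records are already to be abstracted, provided that abstraction runs to that visit. The added figure arrives about 3 months later than the 6-month one and will probably be lower.

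The change does not extend to survey-only participants: section 9.h gives them a single contact with the study, so they have no exit visit. Since section g.i takes retention from the surveys and section e.vii from the cohort, the revised text should say that this measure belongs to the cohort.
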